8.2.1 Definitions

Response and progression will be evaluated in this study using the new international criteria proposed by the Response Evaluation Criteria in Solid Tumors (RECIST 1.0) Committee[67]. Changes in only the largest diameter (unidimensional measurement) of the tumor lesions are used in the RECIST criteria. Note: Lesions are either measurable or non-measurable using the criteria provided below. The term “evaluable” in reference to measurability will not be used because it does not provide additional meaning or accuracy.

8.2.1.1 Measurable disease

Measurable lesions are defined as those that can be accurately measured in at least one dimension (longest diameter to be recorded) as ≥ 20 mm with conventional techniques (CT, MRI, x-ray) or as ≥ 10 mm with spiral CT scan. All tumor measurements must be recorded in millimeters (or decimal fractions of centimeters).

8.2.1.2 Non-measurable disease

All other lesions (or sites of disease), including small lesions (longest diameter <20 mm with conventional techniques or <10 mm using spiral CT scan), are considered non-measurable disease. Bone lesions, leptomeningeal disease, ascites, pleural/pericardial effusions, lymphangitis cutis/pulmonis, inflammatory breast disease, abdominal masses (not followed by CT or MRI), and cystic lesions are all non-measurable.

8.2.1.3 Target lesions

All measurable lesions up to a maximum of five lesions per organ and 10 lesions in total, representative of all involved organs, should be identified as **target lesions** and recorded and measured at baseline. Target lesions should be selected on the basis of their size (lesions with the longest diameter) and their suitability for accurate repeated measurements (either by imaging techniques or clinically). A sum of the longest diameter (LD) for all target lesions will be calculated and reported as the baseline sum LD. The baseline sum LD will be used as reference by which to characterize the objective tumor response.

8.2.1.4 Non-target lesions

All other lesions (or sites of disease) should be identified as **non-target lesions** and should also be recorded at baseline. Non-target lesions include measurable lesions that exceed the maximum numbers per organ or total of all involved organs as well as non-measurable lesions. Measurements of these lesions are not required, but the presence or absence of each should be noted throughout follow-up.

8.2.2 Guidelines for Evaluation of Measurable Disease

All measurements should be taken and recorded in metric notation using a ruler or calipers. All baseline evaluations should be performed as closely as possible to the beginning of treatment and never more than 4 weeks before the beginning of the treatment.

Note: Tumor lesions that are situated in a previously irradiated area might or might not be considered measurable.

The same method of assessment and the same technique should be used to characterize each identified and reported lesion at baseline and during follow-up. Imaging-based evaluation is preferred to evaluation by clinical examination when both methods have been used to assess the

antitumor effect of a treatment.

Clinical lesions. Clinical lesions will only be considered measurable when they are superficial (e.g., skin nodules and palpable lymph nodes). In the case of skin lesions, documentation by color photography, including a ruler to estimate the size of the lesion, is recommended.

Chest x-ray. Lesions on chest x-ray are acceptable as measurable lesions when they are clearly defined and surrounded by aerated lung. However, CT is preferable.

Conventional CT and MRI. These techniques should be performed with cuts of 10 mm or less in slice thickness contiguously. Spiral CT should be performed using a 5 mm contiguous reconstruction algorithm. This applies to tumors of the chest, abdomen, and pelvis. Head and neck tumors and those of extremities usually require specific protocols.

Ultrasound (US). When the primary endpoint of the study is objective response evaluation, US should not be used to measure tumor lesions. It is, however, a possible alternative to clinical measurements of superficial palpable lymph nodes, subcutaneous lesions, and thyroid nodules. US might also be useful to confirm the complete disappearance of superficial lesions usually assessed by clinical examination.

Endoscopy, Laparoscopy. The utilization of these techniques for objective tumor evaluation has not yet been fully and widely validated. Their uses in this specific context require sophisticated equipment and a high level of expertise that may only be available in some centers. Therefore, the utilization of such techniques for objective tumor response should be restricted to validation purposes in reference centers. However, such techniques may be useful to confirm complete pathological response when biopsies are obtained.

Cytology, Histology. These techniques can be used to differentiate between partial responses (PR) and complete responses (CR) in rare cases (e.g., residual lesions in tumor types, such as germ cell tumors, where known residual benign tumors can remain).

The cytological confirmation of the neoplastic origin of any effusion that appears or worsens during treatment when the measurable tumor has met criteria for response or stable disease is mandatory to differentiate between response or stable disease (an effusion may be a side effect of the treatment) and progressive disease.

8.3 Response Criteria

8.3.1 Evaluation of target lesions

Complete Response (CR): Disappearance of all target lesions

Partial Response (PR): At least a 30% decrease in the sum of the longest diameter (LD) of target lesions, taking as reference the baseline sum LD

Progressive Disease (PD): At least a 20% increase in the sum of the LD of target lesions, taking as reference the smallest sum LD recorded since the treatment started or the appearance of one or more new lesions

Stable Disease (SD): Neither sufficient shrinkage to qualify for PR nor sufficient increase to qualify for PD, taking as reference the smallest sum LD since the

treatment started

8.3.2 Evaluation of non-target lesions

Complete Response (CR):	Disappearance of all non-target lesions and normalization of tumor marker level
Incomplete Response/ Stable Disease (SD):	Persistence of one or more non-target lesion(s) and/or maintenance of tumor marker level above the normal limits
Progressive Disease (PD):	Appearance of one or more new lesions and/or unequivocal progression of existing non-target lesions

Although a clear progression of “non-target” lesions only is exceptional, in such circumstances the opinion of the treating physician should prevail, and the progression status should be confirmed at a later time by the review panel (or study chair).

Note: If tumor markers are initially above the upper normal limit, they must normalize for a patient to be considered in complete clinical response.

8.3.3 Evaluation of best overall response

The best overall response is the best response recorded from the start of the treatment until disease progression/recurrence (taking as reference for progressive disease the smallest measurements recorded since the treatment started). The patient's best response assignment will depend on the achievement of both measurement and confirmation criteria (see section 11).

Target Lesions	Non-Target Lesions	New Lesions	Overall Response
CR	CR	No	CR
CR	Incomplete response/SD	No	PR
PR	Non-PD	No	PR
SD	Non-PD	No	SD
PD	Any	Yes or No	PD
Any	PD	Yes or No	PD

Target Lesions	Non-Target Lesions	New Lesions	Overall Response
Any	Any	Yes	PD

Note:

- X Patients with a global deterioration of health status requiring discontinuation of treatment without objective evidence of disease progression at that time should be classified as having “symptomatic deterioration.” Every effort should be made to document the objective progression, even after discontinuation of treatment.
- X In some circumstances, it may be difficult to distinguish residual disease from normal tissue. When the evaluation of complete response depends on this determination, it is recommended that the residual lesion be investigated (fine needle aspirate/biopsy) before confirming the complete response status.

8.3.4 Confirmatory Measurement/Duration of Response

8.3.4.1 Duration of overall response

The duration of overall response is measured from the time measurement criteria are met for CR or PR (whichever is first recorded) until the first date that recurrent or progressive disease is objectively documented (taking as reference for progressive disease the smallest measurements recorded since the treatment started).

The duration of overall CR is measured from the time measurement criteria are first met for CR until the first date that recurrent disease is objectively documented.

8.3.4.2 Duration of Stable Disease

Stable disease is measured from the start of the treatment until the criteria for progression are met, taking as reference the smallest measurements recorded since the treatment started.

8.3.5 Biochemical Response Criteria –PSA measurements (PSA Consensus Criteria) [68]

8.3.5.1 PSA Decline of $\geq 50\%$

A decline of PSA of at least 50% (confirmed by a second value at least 4 weeks after the first) with no other evidence of disease progression.

8.3.5.2 PSA Progression (all progression dates require to be confirmed by a second value after the first no sooner than 4 weeks after the initial measurement)

A 50% increase in PSA over nadir (confirmed by a second reading four weeks later) in patients whose PSA has fallen by at least 50%. PSA increase must be at least 5ng/ml.

8.3.5.3 A 25% increase in PSA over nadir (confirmed by a second reading) in patients whose PSA has not fallen by at least 50%. PSA increase must be at least 5ng/ml.

8.3.5.4 A 25% increase in PSA over baseline in patients whose PSA has not decreased. PSA increase must be at least 5ng/ml.

8.3.5.5 Time to PSA Progression

The time between the first day of treatment to the day of PSA progression as described in 8.2.5.2 the day of progression is defined as the first study day when the PSA level meets progression criteria (not the day of verification).

8.3.5.6 Patients may continue to receive satraplatin as long as they do not have clear evidence of radiographic or clinical progression.

8.4 Toxicity Criteria

This study will utilize the CTCAE version 3.0 for grading adverse events. A copy of the CTCAE version 3.0 is available at <http://ctep.cancer.gov>. All appropriate treatment areas will have access to a copy of the CTCAE version 3.0.

9 Statistical Analysis

The primary objective of this single arm study is to determine if the presence of a polymorphism which is associated with DNA damage repair may be associated with an impact on the progression free survival of patients with metastatic prostate cancer.

A total of 66 evaluable patients will be accrued to the study and the evaluation will take place based upon the following anticipated characteristics of the trial:

The particular polymorphism of interest, ERCC1, has a WT (CC) prevalence of 19% in Caucasians (n=108) and 77% in African Americans (n=127). (Unpublished data) Based upon an estimate that 15% of projected patients to be enrolled on the study will be African American, the overall percentage of patients expected to have the WT genotype is 28%, and thus 72% are expected to express other genotypes other than wild type (TT or CT). Other studies have suggested that the presence of the WT genotype is associated with potentially lower progression free survival probabilities and that having the other genotypes would convey a more favorable prognosis [69].

This trial will treat all enrolled patients with satraplatin 80 mg/m² dose on days 1-5 of every 35-day cycle plus Prednisone 5 mg twice daily every 35 days, based on the Phase III SPARC trial. Preliminary data from this trial with a similar population of prostate cancer patients treated with the same agent had a 39% 6 month progression-free survival when pain is not included in the determination of PFS. It is unknown whether the results in this trial will be the same, but it will be conservatively estimated that for all patients taken together, the 6 month progression free survival will be the same 39%. If the patients enrolled on the present trial are distributed in the approximately expected proportion of 72% with non-wild type genotypes and 28% wild type, it would be of interest to determine if a modest difference in the proportion of patients who have not progressed by 6 months can be detected on the basis of their genotype. As this is meant to be a pilot investigation, using a one-tailed 0.10 alpha level Fisher's exact test, with 20 patients enrolled who have the wild type and 46 who have other genotypes (approximately a 28:72 split), would provide 80% power to detect a difference between proportions of patients without

progression at 6 months of 20% vs. 50%.

Although the primary endpoint will be determined using a Fisher's exact test, Kaplan-Meier curves with a log-rank evaluation will also be performed, although this will be considered a secondary analysis.

The entire group of 66 patients will also be evaluated using a Kaplan-Meier curve to describe the progression free survival of the group as a whole, as a secondary evaluation as well.

Overall survival will also be determined to the extent possible for the group of 66 patients as a whole and also as a function of the genotype expression described; this will be considered a secondary evaluation.

The trial will be conducted using a single stage design. However, to protect against the unlikely possibility that the agent will be associated with overall progression free survival which is substantially below what is expected based on results from other trials, an early stopping rule will be implemented as follows. After 20 patients have been enrolled and 6 months have passed since the 20th patient has enrolled, the proportion of patients who have attained 6 months without progression will be determined. If this fraction is no greater than 3/20 (15% who have attained 6 month progression free survival), then the trial will cease enrolling further patients because a one-sided 90% upper confidence bound on 3/20 is 30.4%, which would only indicate at best a modest probability of marginal consistency with what would be expected as the overall outcome using this agent. We will also perform genotyping for ERCC1 after the 20th patient, this is to test whether we are achieving the true probability of ERCC1 wild type proportion of 20% as indicated in earlier studies (in Caucasians). If the true probability is as shown, the probability of having 0 or 1 subject with WT genotype is tabled:

True WT proportion	Probability of getting 0 or 1 with WT
0.2	7%
0.1	39%
0.05	74%

Thus, if only 0 or 1 patient out of the first 20 patients should have ERCC1 WT genotype, then this would be more consistent with a 0.05 rather than a 0.20 true rate of WT. If this turns out to be the case, then we would re-evaluate the procedure for enrolling subjects to try to increase the proportion of patients with ERCC1 WT and amend the protocol accordingly.

Toxicity of the agent will also be tabulated for all patients taken as a group, and potentially by type of polymorphism genotype expression in the event that this may have some association. The distributions of toxicity identified will be compared informally to data from the same agent in other trials.

This trial will also explore other biologic correlates, as outlined above using genotyping for other DNA repair gene polymorphisms, white blood cell collections, and tumor biopsy, whenever possible. Monthly PSA, CBC, and serum chemistries will be performed at baseline and monthly thereafter, with CT scans and bone scans to be performed at baseline and every 10 weeks of treatment until progression. The comparisons will be made without any correction for multiple comparisons because of the exploratory and secondary nature of the evaluations.

9.1 Sample Size/Accrual Rate

Based on previous efforts in recruiting patients with this disease onto trials at the NCI, it is anticipated that 30 patients per year may be able to enroll onto this protocol. Thus, it is expected that accrual to this trial can be completed in approximately 2.5 years if all 66 patients are to be enrolled.

9.2 Stratification Factors

There are no stratification factors

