2 ELIGIBILITY ASSESSMENT AND ENROLLMENT

2.1 Eligibility Criteria

2.1.1 Inclusion Criteria

2.1.1.1 Patients must have histopathological confirmation of prostate cancer by the Laboratory of Pathology of the NCI or Pathology Department of the National Naval Medical Center or Walter Reed Army Medical Center prior to entering this study. Patients whose pathology specimens are not available may be enrolled in the trial if the patient has a clinical course consistent with prostate cancer and available documentation from an outside pathology laboratory of the diagnosis. In cases where original tissue blocks or archival biopsy material is available, all efforts should be made to have the material forwarded to the research team for use in correlative studies.

2.1.1.2 Patients must have metastatic progressive androgen-independent prostate cancer. There must be radiographic evidence of disease (by CT scan or bone scan) after primary treatment that has continued to progress despite hormonal agents. Progression requires that a measurable lesion is expanding, new lesions have appeared, and/or that PSA is continuing to rise on successive measurements. Patients must have progressive disease after receiving 1 prior docetaxel-based cytotoxic chemotherapy. Patients on flutamide for the prior 6 months must have disease progression at least 4 weeks after withdrawal. Patients on bicalutamide or nilutamide must have progression at least 6 weeks after withdrawal.

2.1.1.3 Patients may only have received 1 prior cytotoxic chemotherapy. For the purpose of this study, multiple courses of a taxane-based regimen may count as a single regimen. Multiple courses of a non-taxane agent or a combination chemotherapy regimen, administered in a similar fashion may count as a single regimen.

2.1.1.4 Patients must have a life expectancy of more than 3 months.

2.1.1.5 Patients must have a performance status of 0 to 2 according to the ECOG criteria.

2.1.1.6 Patients must have adequate organ function as defined below:

Leukocytes	$\geq 3,000/\mu\text{l}$
Absolute Neutrophil Count	$\geq 1,500/\mu\text{l}$
Platelets	$\geq 100,000/\mu\text{l}$
Total bilirubin	$\leq 1.5 \times$ institutional upper limits of normal*
AST(SGOT) and ALT(SGPT)	$\leq 2.5 \times$ institutional upper limit of normal
creatinine	$\leq 1.5 \times$ institutional upper limits of normal
OR	
Creatinine clearance	$\geq 60 \text{ mL/min}/1.73 \text{ m}^2$ for patients with creatinine levels above institutional normal.

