2.2.2 Laboratory Evaluation (Baseline- obtained within 16 days prior to enrollment)

- Hematological Profile: CBC with differential and platelet count, PT, aPTT, fibrinogen.
- Biochemical Profile: electrolytes, BUN, creatinine, AST, ALT, alkaline phosphatase, total bilirubin, calcium, phosphorus, albumin, magnesium, uric acid, total protein, glucose, albumin, amylase, lipase, testosterone level.
- PSA (baseline within 7 days prior to enrollment)
- Electrocardiogram (performed within 21 days prior to enrollment); Patients with a history of myocardial infarction or cardiac arrhythmias will undergo evaluation by cardiology.

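### The stated genotype comparisons of PFS are unadjusted although ECOG status and PSA are collected at baseline; one supportive Cox model would use them at almost no cost

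*Protocol*

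**What the plan says.** The primary analysis in section 9 is a comparison of 6-month PFS by ERCC1 genotype, "using a one-tailed 0.10 alpha level Fisher's exact test". The planned groups are 20 wild-type patients and 46 others, and the protocol claims 80% power to separate 6-month progression-free proportions of 20% and 50%. As a secondary analysis, "Kaplan-Meier curves with a log-rank evaluation will also be performed". No covariate or stratum is named for either comparison, and section 9.2 reads in full: "There are no stratification factors".

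Two baseline measures of disease state are available for everyone. Section 5.1 has ECOG status recorded within 16 days of enrolment, and section 2.2.2 lists "PSA (baseline within 7 days prior to enrollment"). Entry is broad on both: "Patients must have a performance status of 0 to 2 according to the ECOG criteria" (section 2.1.1.5), and section 2.1 sets no PSA limit. The trial is single-arm, so nothing balances these factors between genotype groups.

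**The concern.** The primary question is a comparison of two groups formed by genotype, one of them with only about 20 patients. If a few more ECOG 2 or high-PSA patients fall into one group, the unadjusted estimate carries that difference, and a critic can say that the groups simply entered with different disease burden. An adjustment first proposed after the imbalance has been seen would be post hoc and less convincing. If the factors are prognostic, an unadjusted time-to-event comparison is also somewhat less powerful than an adjusted one, and its hazard ratio lies closer to 1. At stake are the precision of the secondary analysis and the credibility of the one realised data set. The validity of the primary test is not in question.

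**Working it through.** **1. The protocol's own figure.** Inputs from section 9: 20 vs 46 patients, 20% vs 50% progression-free at 6 months, one-sided alpha 0.10, Fisher's exact test. Power is the sum, over all pairs of counts (x, y) with one-sided Fisher p ≤ 0.10, of Bin(x; 20, 0.20) × Bin(y; 46, 0.50). The result is 80.4% against the stated 80%, so it reproduces.

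**2. Does chance imbalance damage the primary test?** The same enumeration with equal PFS in both groups gives the actual size: 5.4% at a common PFS of 20%, 6.1% at 39% and 6.4% at 50%. All are below the nominal 10%, so chance imbalance does not inflate the error rate.

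**3. How large can a chance imbalance be?** For a binary factor with prevalence q, the SD of the difference in prevalence between groups is √[q(1−q)(1/20 + 1/46)].
- q = 0.2 (assumed): √(0.16 × 0.0717) = 10.7 points; P(imbalance above 20 points) is about 6%.
- q = 0.3 (assumed): √(0.21 × 0.0717) = 12.3 points; P(imbalance above 20 points) is about 10%.

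If the factor is worth 20 to 30 points of 6-month PFS (assumed), a 1-SD imbalance at q = 0.3 shifts the observed difference by 0.123 × 20 = 2.5 to 0.123 × 30 = 3.7 points, against a design difference of 30.

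**4. What would adjustment gain in a Cox model?** The protocol gives no prognostic strengths and no ECOG distribution. The assumptions are 20% ECOG 2, an ECOG hazard ratio of 1.5 to 2.5, and a PSA hazard ratio of 1.3 to 1.8 per SD. The simulation used 20 vs 46 patients, one-sided 0.10, Efron ties, scans every 10 weeks, censoring at week 60 and 1,500 trials per setting. The SE of each figure is at most √(0.931 × 0.069/1500) = 0.7 points for the runs with 20% vs 50% preserved, and up to √(0.834 × 0.166/1500) = 1.0 point for the others.

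The protocol's 20% and 50% are whole-group proportions. With no other prognostic factor they imply a hazard ratio of ln 0.20 / ln 0.50 = 2.32. Once ECOG and PSA matter, holding 2.32 as the hazard ratio within covariate levels shrinks the whole-group difference, so that setting no longer represents the design effect. Both versions are shown as unadjusted / adjusted power.

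| ECOG HR, PSA HR per SD | 20% vs 50% preserved | HR 2.32 held within covariate levels |
|---|---|---|
| 1.5, 1.3 | 96.1% / 97.1% (+1.0) | 92.6% / 94.9% (+2.3) |
| 2.0, 1.5 | 95.5% / 98.0% (+2.5) | 88.7% / 93.1% (+4.4) |
| 2.5, 1.8 | 93.1% / 98.1% (+5.0) | 83.4% / 91.1% (+7.7) |

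With neither factor prognostic, two separate Cox runs gave 95.9% / 95.1% and 96.1% / 95.9%, a loss of 0.8 and 0.2 points.

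**5. Cross-check on the binary endpoint.** Linear models of 6-month status (20,000 trials per setting; one binary factor with 30% prevalence, one continuous factor; 20% vs 50% preserved) gave:
- odds ratio 2, log-odds 0.3 per SD: 86.7% to 87.5%;
- odds ratio 3, log-odds 0.5 per SD: 87.0% to 89.0%;
- odds ratio 4, log-odds 0.8 per SD: 87.0% to 90.6%;
- no prognostic effect: 86.3% to 86.0%.

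The gain is about 1 to 3.5 points, in line with step 4.

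**6. Can the data carry the model?** At the design rates, 20 × 0.20 + 46 × 0.50 = 27 patients are progression-free at 6 months, so about 66 − 27 = 39 have progressed. Three model terms give about 39/3 = 13 events per term by then.

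**The case against.** The strongest objection is that a supportive adjusted model is commonly left to a statistical analysis plan, and none is shown here. That stands in part: if such a plan already contains the model, the point is met. But section 9 does name its genotype analyses of PFS, and all of them are unadjusted, so this is a comment on a stated analysis.

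Four stronger readings are tempting, and the documents do not support them.
- **That section 9.2 rules out adjustment.** It says there are no strata, which is unremarkable in a single-arm trial. It does not bar covariates.
- **That the primary test loses power or validity.** Its 80% was calculated for the unadjusted test and reproduces, and its actual size is about 6%. The gains in step 4 compare two Cox models, neither of which carries a power claim in the protocol. The pull of a hazard ratio toward 1 when a prognostic factor is left out does not apply to a difference in 6-month proportions when the factor is balanced.
- **That 3 to 8 points of power are at stake.** Gains of that size arise only when 2.32 is held within covariate levels, which departs from the protocol's whole-group 20% vs 50%.
- **That adjusting for ECOG and PSA would make the groups comparable.** The only factor that the protocol itself ties to genotype is race. From section 9 (wild type 19% and 77%, 15% African American), 0.15 × 0.77 / 0.277 = 42% of wild-type but 0.15 × 0.23 / 0.723 = 5% of other patients would be African American.

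It is also fair to say that the trial is described as a pilot and that, at an assumed 20%, only 20 × 0.20 = 4 wild-type patients would be ECOG 2. Both limit what the adjusted estimate can show. Neither is a reason to leave collected data unused.

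**Conclusion.** The point holds as a minor improvement. The stated genotype comparisons of PFS are unadjusted, the groups are not randomised, and two baseline measures of disease state go unused. An imbalance in either would remain in the estimate, and the secondary time-to-event comparison forgoes some precision. The gain from adjustment in a supportive Cox model is about 1 to 5 power points at the protocol's 20% vs 50%, and the loss is about 1 point or less if neither factor is prognostic. Those figures depend on the assumed 20% ECOG 2 and hazard ratios of 1.5 to 2.5 (ECOG) and 1.3 to 1.8 per SD (PSA). No number in the protocol is wrong, and the primary test stands as planned. Race needs its own treatment.

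**What to change.** Keep Fisher's exact test as the primary analysis. Add one sentence to section 9 that pre-states a supportive Cox model for PFS with three terms: genotype (CC vs CT/TT), ECOG (0-1 vs 2) and log baseline PSA. Report the adjusted hazard ratio and its interval beside the unadjusted log-rank result. In section 9.2, make clear that the absence of strata does not exclude this model. The cost is one sentence and one extra model on data already collected. The sample size, the primary test and its power statement do not change.
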